The CUH IPC Guideline² states all symptomatic patients who are to be admitted from ED must have Cepheid monoplex POCT PCR assay performed to test for SARS-CoV-2. During the winter months when there is a high prevalence of seasonal respiratory viruses, a Cepheid multiplex POCT PCR assay is utilised instead which tests for influenza A, influenza B, Respiratory Syncytial Virus (RSV) and SARS-CoV-2. Hospital inpatients who did not exhibit respiratory symptoms at admission but go on to develop them are tested using a SARS-CoV-2 POCT PCR (SAMBA) test and also UK HSA laboratory respiratory PCR swab Luminex analysis which tests for human adenovirus, seasonal coronaviruses, human bocavirus, human metapneumovirus, influenza A (H1, H3, 2009 H1N1), influenza B, parainfluenza (1-4), picornaviruses (rhino/ enterovirus), RSV A and B, *Chlamydia pneumoniae*, *Legionella pneumophila* and *Mycoplasma pneumoniae*. Patients who are admitted to hospital after testing negative on the Cepheid POCT in the ED but with ongoing clinical concern for respiratory viral infection, may also undergo additional UK HSA laboratory respiratory virus PCR testing.

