This study aims to recruit participants during the winter months, when the gold standard POCT device used at CUH is the Cepheid multiplex PCR assay (known as GeneXpert). This test can produce results in around 40 minutes to an hour. The advantage of utilising the Logicore System is that it can test for 2 additional pathogens in roughly the same amount of time as Cepheid (it takes 63 minutes to produce the results) but is expected to be more sensitive to the pathogens (for example, the minimum limit of detection is 131 copies/mL for SARS-CoV-2 using Cepheid³ but is expected to be only 100 copies/mL for the same pathogen using the Logicore System). This could alleviate the need for additional UK HSA laboratory testing if a patient was admitted following a negative Cepheid test but continued to exhibit respiratory symptoms, as it is more likely the pathogen would be identified in the initial Logicore System testing process. The CUH IPC Guideline instructs that patients with suspected respiratory infection should be isolated while further UK HSA lab PCR testing is performed. Therefore, the improved sensitivity in diagnostic capability could reduce the need for unnecessary isolation of patients as there would be reduced requirement for the secondary HSA testing. Conversely, the improved turnaround time would ensure rapid instigation of appropriate isolation procedures when a patient has positive initial results to reduce the spread of infection in the ED, in conjunction with quicker treatment of patients with targeted therapeutics medicinal products.

This study aims to produce evidence to support the Logicore System claims of increased sensitivity and specificity, whilst maintaining accuracy, and reduced turnaround times Version 1.0 dated 09/OCT/2025 CONFIDENTIAL Page 13 of 49

compared to current practice, and to provide the Trust with a Cost Benefit analysis from assessment with the Logicore System.

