B. If the Cepheid and Logicore System results are positive for different pathogens, it is not possible to test the participant again as the result from the gold standard Cepheid test will be taken as correct and used to determine appropriate treatment. The participant would not have repeat testing according to standard care. If the Logicore System result is positive for one of the pathogens that Cepheid does not test for (i.e. *Mycoplasma pneumoniae* or human adenovirus), it will be taken to be a true positive result. If however, the Logicore System result is positive for a different pathogen that Cepheid does test for (i.e. Flu A, Flu B, RSV or SARS-CoV-2) but it is not the same pathogen that is positive according to the Cepheid result, the Logicore System result will be classed as a false positive.

C. If the Cepheid result is negative but the Logicore System result is positive, and the participant still exhibits clinical symptoms of respiratory infection requiring diagnostic testing as per CUH Trust Infection Prevention and Control Guideline, a second single swab will be taken from the participant and used for second-line testing as per the CUH Trust standard UK HSA laboratory respiratory virus PCR testing policy. The result from the second-line testing will then be compared to the initial Logicore System result. If the Logicore System result agrees with the second-line result, it will be classed as a true positive. If it does not match the pathogen from the second-line testing, the initial Logicore System result will be classed as a false positive.

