13.5.3 Study Sample Collection and Testing Process

Study staff undertaking the sample collection will wear appropriate personal protective equipment (PPE) for the risk exposure at all times, in line with CUH local guidelines for Infection Prevention and Control. To eliminate potential differences in the samples being tested, two nasopharyngeal swabs will be collected simultaneously. One swab will be tested by the gold standard Cepheid multiplex POC test (i.e. standard of care diagnostic testing as required by CUH Trust IPC policy) and the other with the novel Logicore System multiplex POC device. The Logicore System swab will be tested using a specific Logicore System buffer which will be provided for use in a closed vial by the Sponsor. The testing of each specimen (Cepheid or Logicore) must begin within 20 minutes from the time of swab collection, according to the specimen processing guidelines. There is no need to store the swabs/buffer solutions on ice. These can remain at ambient temperature for storage.

The Cepheid POCT is done in the laboratories above the ED. The Logicore System (i.e. the Analytical Module into which the Respiratory Pathogen Panel cartridge is loaded for analysis and the portable Operation Module with display screen, into which the cartridge details and participant anonymised details are input) will be located in a secure clinical area within the ED, with controlled access.

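### Rule C settles one discordant cell with a later, separate swab and no unconfirmed class, so Logicore PPV and specificity depend on whether a detection repeats

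*Protocol*

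**What the plan says.** Rule C, under Figure 1 in Protocol section 11.0, opens: "If the Cepheid result is negative but the Logicore System result is positive, and the participant still exhibits clinical symptoms of respiratory infection". If further testing is then required under Trust policy, "a second single swab will be taken from the participant and used for second-line testing". Two outcomes are named. When both tests find the same pathogen, Logicore is credited with a true positive. The other outcome reads: "If it does not match the pathogen from the second-line testing, the initial Logicore System result will be classed as a false positive". A negative second-line result is not named, though false positive is its natural reading. No interval is set and the original specimen is not retested.

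The neighbouring rules differ. Rule A scores Cepheid-positive, Logicore-negative as a Logicore false negative with no retest. Rule B applies when Cepheid is positive for another pathogen, and accepts a Logicore finding of Mycoplasma pneumoniae or adenovirus as true with no check.

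Section 13.5.3 gives the reason for paired sampling: "To eliminate potential differences in the samples being tested, two nasopharyngeal swabs will be collected simultaneously". Section 14.1 repeats that argument. The 2 x 2 table in section 14.5.1 classes every test-positive, standard-negative result as a false positive.

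On timing, section 13.5.1 places the additional swab at the ED visit. As background on Trust practice, section 7.1 adds that "Patients who are admitted to hospital after testing negative on the Cepheid POCT in the ED but with ongoing clinical concern" may also have the laboratory test. The data list in section 11.0 includes the time of nasopharyngeal swabs but does not say whether the second-line swab is covered.

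**The concern.** The plan treats simultaneity as what makes two results comparable, then decides the disputed cases with a specimen that lacks it. The trigger needs a Logicore result, so the deciding swab comes at least about 63 minutes after that test starts. It is a fresh specimen on a different assay. Section 13.5.4 has positive results passed to the care team, and section 8.2 says that a Logicore-only detection may bring earlier treatment, so treatment could precede it.

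A non-match can mean that Logicore was wrong, or that a true detection did not repeat. The protocol gives a reason to expect the second: for SARS-CoV-2, "the minimum limit of detection is 131 copies/mL for SARS-CoV-2 using Cepheid" but is "expected to be only 100 copies/mL for the same pathogen using the Logicore System". Extra detections that arise this way lie near the detection limit, where a repeat swab is least dependable. Rule C scores both explanations as device error, and nothing in the results would show how many there were of each.

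The rule is also one-sided, because only the cell in which Logicore alone is positive gets a second look. PPV and specificity, both part of the primary endpoint, thus depend on the later swab in a way that a single reported figure hides.

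**Working it through.** **The plan's own figure.** Section 14.3.1: n = 1.96² × 0.95 × 0.05 / 0.10² = 18.25, rounded up to 19; 19 / 0.05 = 380; plus 20 gives 400. This reproduces and is not affected by the point.

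**Inputs from the protocol.** N = 400; prevalence 5%, 10% or 15% (section 14.1 table); Logicore sensitivity 0.95 (section 14.3.1).

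**Assumptions, not in the protocol.** Cepheid sensitivity c = 0.90 or 0.95; Logicore specificity 0.99; Cepheid and second-line specificity 1; independent errors; every discordant participant retested; and a probability r that a true Logicore-only detection repeats on the later swab.

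**Formulae for one shared pathogen**, with T = N × prevalence:
- positive on both: T × 0.95 × c
- true Logicore-only: d = T × 0.95 × (1 − c)
- false Logicore-only: f = (N − T) × 0.01
- rule C: TP = both + d × r; FP = f + d × (1 − r)
- Cepheid alone is the case r = 0

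All Logicore positives number T × 0.95 + f, so rule C puts PPV below the truth by d(1 − r) / (T × 0.95 + f) and above the Cepheid-only figure by d × r / (T × 0.95 + f).

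**Worked case: prevalence 10%, c = 0.90, r = 0.5.** T = 40; both = 34.2; d = 3.8; f = 3.6; Logicore positives = 41.6. True negatives are 356.4, plus 0.2 infected participants negative on both tests, giving 356.6 in the table.
- Truth: PPV 38 / 41.6 = 0.913; specificity 0.990
- Rule C: PPV 36.1 / 41.6 = 0.868; specificity 356.6 / 362.1 = 0.985
- Cepheid alone: PPV 34.2 / 41.6 = 0.822; specificity 356.6 / 364.0 = 0.980

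**All six cases at r = 0.5:**

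| Prevalence | c | d | PPV: truth / rule C / Cepheid alone | Specificity: truth / rule C / Cepheid alone |
|---|---|---|---|---|
| 5% | 0.90 | 1.90 | 0.833 / 0.792 / 0.750 | 0.9900 / 0.9875 / 0.9851 |
| 5% | 0.95 | 0.95 | 0.833 / 0.812 / 0.792 | 0.9900 / 0.9888 / 0.9875 |
| 10% | 0.90 | 3.80 | 0.913 / 0.868 / 0.822 | 0.9900 / 0.9848 / 0.9797 |
| 10% | 0.95 | 1.90 | 0.913 / 0.891 / 0.868 | 0.9900 / 0.9874 / 0.9848 |
| 15% | 0.90 | 5.70 | 0.944 / 0.897 / 0.849 | 0.9900 / 0.9818 / 0.9737 |
| 15% | 0.95 | 2.85 | 0.944 / 0.920 / 0.897 | 0.9900 / 0.9859 / 0.9818 |

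About 1 to 6 true Logicore-only detections are expected per pathogen. Rule C puts PPV 2.1 points (0.475 / 22.8) to 4.7 points (2.85 / 60.4) below the truth, and specificity 0.1 to 0.8 points below. At r = 0.5 the PPV gain over Cepheid alone is the same 2.1 to 4.7 points, because half of d moves each way.

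**The two extra pathogens.** Cepheid gives no result for them. If all k Logicore detections reaching rule C are true, rule C's expected PPV among them is k × r / k = r. With k = 20 for illustration (5% of 400, the share used in section 14.3.4, although that share is defined as also reflex-positive), r = 0.5 gives 10/20 = 50% and r = 0.9 gives 18/20 = 90%.

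**Dropping non-matches.** In the worked case this leaves 36.1 / 36.1 = 100%, although 3.6 Logicore results are false.

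**The case against.** The strongest reply is that rule C helps Logicore. It starts only when the simultaneous Cepheid swab is negative, so for the four shared pathogens a non-match agrees with that swab. Section 14.5.1 would call those results false positives anyway, and rule C can only move some of them to true positive. This stands. A reader might infer that the later swab overrules the simultaneous comparison to Logicore's detriment. The text does not support that: the later swab overrules Cepheid only on a match, and the downward error exists only relative to an unknown truth.

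Three further limits also stand:
- A reader might infer that the superior-sensitivity claim is undermined. Section 14.5.1 rests that claim on McNemar's test of paired positives, which does not use rule C labels.
- A reader might infer a gap of days. Section 13.5.1 puts the swab at the ED visit; section 7.1 describes general practice. What can be said is that no limit is stated.
- The only two-device comparison of detection limits is for SARS-CoV-2, a gap of 131/100 = 1.3-fold, and section 7.1's list of Luminex targets does not name that virus. The low-load argument is therefore a plausible mechanism, not a demonstrated one.

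An analysis plan not at hand might add sensitivity analyses. The classification itself, however, is fixed in the protocol, and data on the deciding swab must be collected during recruitment.

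**Conclusion.** The point holds in a limited form. Rule C resolves one discordant cell only, with a non-contemporaneous swab on another assay, no stated interval and no unconfirmed class. Its error runs downward relative to the truth and its shift runs upward relative to Cepheid alone, so it cannot be described simply as a bias against the device.

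For the shared pathogens the size is modest: about 2 to 5 PPV points and under 1 specificity point below the truth, on the assumptions listed, chiefly r = 0.5 and Cepheid sensitivity 0.90 to 0.95. A reader might infer a far larger effect by supposing, say, ten true Logicore-only detections beside 19 Cepheid positives. That would imply Cepheid sensitivity of at most 19/29 = 66%, which nothing in the protocol supports.

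The effect is largest for Mycoplasma pneumoniae and adenovirus, where the class rests wholly on the later swab under rule C while rule B accepts the same finding unchecked. These two lie outside the four-pathogen primary endpoint, but cost per additional case detected (section 14.2.4) depends on how they are classed.

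**What to change.** In rule C, record a non-match, including a negative second-line result, as unconfirmed, and show the count per pathogen. For each shared pathogen report PPV and specificity three ways:
- (a) against simultaneous Cepheid alone
- (b) after rule C, with unconfirmed counted as false positive
- (c) after rule C, with unconfirmed counted as true positive, labelled as an upper bound

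For the two extra pathogens report (b) and (c). In the worked case PPV would read 0.822, 0.868 and 1.000, with the truth (0.913) between (b) and (c). Bound (c) is near 100% by design, since only rule B false positives remain in it, so it must not be read as an estimate.

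Do not use an analysis that drops only the unconfirmed results. It removes genuine device errors, keeps the confirmed detections and forces PPV towards 100% while looking like an estimate.

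Record the time of the second-line swab and any antimicrobial or antiviral given before it. These data will not separate the two explanations in a single case, but they let readers judge how far a non-match counts against the first result.

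The cost is a changed sentence in rule C, two eCRF fields and extra table rows, best settled before recruitment. The downside is that PPV and specificity are reported as a range.

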The current gold standard POCT at CUH is Cepheid and the second-line PCR test is Luminex, as specified in their IPC Guideline. However, it must be noted that this study is taking place in a real-world setting which may be subject to change due to NHS supply issues, purchasing changes or other factors outside the control of the ED research team. This has been considered during the design of this protocol. If the second-line testing device happens to change during the course of recruiting participants into this study, the replacement second-line device will still need to test for the 2 additional pathogens that the Logicore System tests for. If the second-line testing device changes during the study, the sample collection and testing process shown in Figure 1 will not change. Thus, the Logicore System results will always be compared to the CUH gold standard POCT and when required, to the standard of care second-line testing device that is being used to identify infectious cases in the ED.

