20.0 APPENDICES

20.1 Appendix 1 – Details of Equipment Used in the Study

The gold standard in vitro diagnostic device used at CUH, is Cepheid POCT (GeneXpert).

Following a negative Cepheid result, if a patient still exhibits clinical symptoms of respiratory infection, the standard second-line testing device is Luminex NxTag, as per CUH Trust Infection Prevention and Control Guideline at the time of devising this protocol.

The IVDD that is the subject of this investigation is the Logicore System.

The Logicore POCT System will always be assessed against the gold standard first-line POCT and standard of care second-line testing devices in line with the Trust IPC policy.

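### For re-swabbed participants, the second-line panel as listed cannot confirm a Logicore-only SARS-CoV-2 result, so section 11.0 item C classes it as a false positive whatever the truth

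*Protocol*

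**What the plan says.** **The adjudication rule.** Protocol section 11.0, item C under Figure 1, begins: "If the Cepheid result is negative but the Logicore System result is positive, and the participant still exhibits clinical symptoms of respiratory infection". If testing is also required under Trust policy, a second swab is taken and "used for second-line testing as per the CUH Trust standard UK HSA laboratory respiratory virus PCR testing policy". Agreement makes the Logicore result a true positive. Otherwise: "If it does not match the pathogen from the second-line testing, the initial Logicore System result will be classed as a false positive". There is no category for a target that the second-line test does not measure.

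**The arbiter.** Section 11.0 states: "The current gold standard POCT at CUH is Cepheid and the second-line PCR test is Luminex". Appendix 1 (20.1) agrees: "the standard second-line testing device is Luminex NxTag".

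**What the arbiter covers.** Section 7.1 describes "Luminex analysis which tests for human adenovirus, seasonal coronaviruses, human bocavirus, human metapneumovirus", and the list goes on to influenza A and B, parainfluenza, picornaviruses, RSV A and B, and three bacteria including *Mycoplasma pneumoniae*. SARS-CoV-2 is not on it. The same sentence gives SARS-CoV-2 a separate test (SAMBA), for inpatients whose symptoms begin after admission. For patients admitted after a negative Cepheid test in the ED, section 7.1 mentions only UK HSA laboratory PCR.

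**If the arbiter changes.** Section 11.0 says "the replacement second-line device will still need to test for the 2 additional pathogens that the Logicore System tests for". That names *M. pneumoniae* and adenovirus coverage as the condition and sets none for SARS-CoV-2.

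**Where the classification feeds in.** SARS-CoV-2 is one of the four shared infections in the primary endpoint (14.2.1). Section 14.5.1 derives sensitivity, specificity, PPV, NPV and likelihood ratios from a 2 x 2 table per infection, in which test positive with standard negative is a false positive.

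**The concern.** Item C exists to separate true extra detections by Logicore from errors. It can do so only for pathogens that the second-line test measures. On the protocol's own list, five of Logicore's six targets can be confirmed and SARS-CoV-2 cannot. A test that does not look for SARS-CoV-2 will never return it, and the rule reads that silence as disagreement.

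The affected pathogen matters. The primary objective (9.1) is increased sensitivity with PPV, NPV and specificity maintained. SARS-CoV-2 is the only pathogen for which the protocol gives a comparative detection limit (100 against 131 copies/mL, sections 7.1 and 8.2). Extra SARS-CoV-2 detections are thus something the protocol leads one to expect, and the rule would score those it adjudicates as errors. The error runs in one direction and a larger sample does not reduce it.

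**Working it through.** **1. The plan's own figures.** Section 14.3.1: n = Z²P(1−P)/d² = 1.96² × 0.95 × 0.05 / 0.10² = 18.2, rounded up to 19. At the lowest prevalence, 19/0.05 = 380, raised to 400. These reproduce. At the roughly 10% SARS-CoV-2 prevalence in section 14.1, 19/0.10 = 190, also as tabled. The point does not depend on these figures; they supply the counts in step 3.

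**2. Tracing a Logicore-positive SARS-CoV-2 result that Cepheid does not report.**

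| Situation | Governing text | Class |
|---|---|---|
| Cepheid negative, re-swabbed | 11.0 item C; Luminex as listed cannot return SARS-CoV-2 | False positive |
| Cepheid negative, not re-swabbed | Item C gives no class | False positive only if the 14.5.1 table is built on Cepheid |
| Cepheid positive for another shared pathogen | 11.0 item B | False positive, for a reason unrelated to the panel |

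The panel gap drives only the first row. In that row the chance of confirmation is zero whether or not the infection is real.

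**3. Illustration of size.** Inputs from the protocol: 400 participants, 10% prevalence, 95% sensitivity. Cepheid positives: 400 × 0.10 = 40. Cepheid negatives: 360. Concordant positives: 40 × 0.95 = 38. The number of true Logicore-only detections is not in the documents. A range of 2 to 5 is assumed, with no analytical false positives and every such participant re-swabbed.

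| Measure for Logicore | 2 extra, as ruled | 5 extra, as ruled | If confirmed |
|---|---|---|---|
| PPV | 38/40 = 95.0% | 38/43 = 88.4% | 100% |
| Specificity | 358/360 = 99.4% | 355/360 = 98.6% | 100% |
| Positive likelihood ratio | 0.95/(2/360) = 171 | 0.95/(5/360) = 68.4 | unbounded (no false positives) |
| Sensitivity | 38/40 = 95.0% | 38/40 = 95.0% | 40/42 = 95.2% or 43/45 = 95.6% |

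Cepheid's sensitivity is 40/40 = 100% as ruled, because nothing it misses can be confirmed. With confirmation it would be 40/42 = 95.2% or 40/45 = 88.9%. With 5 true extra detections the comparison should read 95.6% against 88.9% in Logicore's favour; as ruled it reads 95.0% against 100%.

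**4. What does not change.** McNemar's test in section 14.5.1 compares raw positive and negative results. With 2 to 5 Logicore-only and 40 − 38 = 2 Cepheid-only results, the discordant counts are the same whatever label item C attaches.

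**The case against.** **A reader might infer that every Logicore-only SARS-CoV-2 detection is forced to be a false positive by the panel gap.** The documents do not support that. Item C applies only to participants who remain symptomatic and need testing under Trust policy, and section 13.5.1 says the extra swab may not be required. Those not re-swabbed receive no class from item C. It can also be argued that the non-match sentence presupposes a pathogen was found, leaving a negative Luminex result unclassified. That narrows the certainty of the false-positive label, but on neither reading can the result become a true positive.

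**A reader might infer that the superiority comparison is biased.** It is not: McNemar's test ignores the adjudicated label. The explicit superiority hypothesis (14.2.4) concerns RSV, which Luminex covers.

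**The same PPV loss could arise with a perfect arbiter.** This stands. If the 14.5.1 tables use Cepheid alone, as section 14.1 suggests in declining a composite reference, Logicore-only positives for all four shared pathogens are false positives. The fix must therefore settle which classification the tables use.

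**The target list may be incomplete.** It sits in the Background, in a sentence about inpatients who develop symptoms after admission, and the Trust guideline is not available here. This also stands as a limit. But the protocol names Luminex as the arbiter and gives only this list.

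**The size is assumed.** It is. The documents give two detection limits and nothing on how many patients fall between them.

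**Conclusion.** The point holds for re-swabbed, Cepheid-negative participants. For them, a Logicore-only SARS-CoV-2 positive cannot be confirmed, and the non-match is classed as a false positive whatever the truth. The replacement clause in section 11.0 would allow a new arbiter with the same gap. To the extent that item C feeds the accuracy estimates, adjudicated SARS-CoV-2 specificity, PPV and positive likelihood ratio are too low, and adjudicated sensitivity cannot show a gain over Cepheid.

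On the illustrative counts, specificity loses 0.6 to 1.4 percentage points and PPV 5.0 to 11.6 points. These figures rest on an assumed 2 to 5 true extra detections, no analytical false positives, and re-swabbing of all of them. They cannot be attributed to the panel gap alone until the reference for the 2 x 2 tables is fixed. The conclusion also assumes that the section 7.1 target list is complete. As written, the rule gives a wrong answer for a primary-endpoint pathogen and should be corrected before recruitment.

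**What to change.** 1. **Section 11.0, item C.** Apply the false-positive label only to pathogens that the second-line test covers. Class a Logicore-only positive for an uncovered target as unresolved, unless a SARS-CoV-2 PCR result from routine care exists. Say how a negative second-line result is classed.
2. **Data collection list, section 11.0.** Add any routine-care SARS-CoV-2 PCR result as a data item; it is not listed now.
3. **Arbiter coverage, section 11.0.** Require any test used for adjudication, current or replacement, to cover the pathogen being adjudicated. If the Trust's second-line testing already includes a SARS-CoV-2 assay, state that instead.
4. **Section 14.5.1.** State whether the 2 x 2 tables use the item C classification or Cepheid alone.
5. **Reporting.** Give specificity and PPV twice, with unresolved results counted as true positives and as false positives.

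The cost is a few sentences, one added data item and a bounding analysis. No new test, additional swab or change to patient care is needed.
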